- As of month 12 subjects in this cohort will be able to see their own PAP measurements for the remaining duration of the study.
- All primary and secondary safety and effectiveness analyses will be performed.

Up to 450 subjects are planned to be enrolled and successfully implanted with the Cordella PA (consisting of subjects from Cohort #2 and Cohort #3 below). These subjects will be the basis for the primary study analysis. Additionally, up to 85 subjects (cross- over from former Control Arm) will continued to be followed in Cohort #1.

To be enrolled into the study, subjects must be receiving stable Guideline Directed Medical Therapy (GDMT) for HF per current American Heart Association (AHA)/American College of Cardiology (ACC) guidelines as standard-of-care for HF therapy in the United States and Europe, with any intolerance documented for at least 30 days. This will be verified by the trial specific PROACTIVE-HF Clinical Eligibility Committee.

Subjects must be diagnosed with heart failure for a minimum of 3 months, are clinically stable, have an increase of NT-proBNP and a HF related hospitalization, HF treatment in a hospital day-care setting, or urgent outpatient clinic HF visit for IV diuretics within 12 month (last hospitalization should be 30 days before Screening /Enrollment)

Potential subjects are to be identified by the Investigator and research staff with the study Inclusion and Exclusion criteria in mind. At Screening, subjects are fully informed on what to expect with study participation to maintain a high study participation retention rate. As part of the study Implant Visit, subjects undergo a training on the at-home use of the Cordella™ Heart Failure System (Cordella System) to ensure compliance with the web-based clinical care management component of the Cordella™ Heart Failure System. Throughout the study, subjects will continue to be followed closely to ensure study compliance as well as continued study participation

At the Screening/ Enrollment Visit, subjects review and sign the informed consent form prior to any study-related procedures performed. Based on Screening Visit results, the Investigator confirms and documents study eligibility for each subject. As part of the study screening process, subjects will be scheduled for a RHC and PA Sensor Implant procedure.

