Sample size calculations for the first secondary endpoint were performed in PASS 2021 and based on an assumed population event rate of 0.55, the sample size of 450 subjects would provide approximately 95% power for the secondary endpoint based on a one-sided 0.025 alpha level. If 406 subjects are followed for 12 months, approximately 95% power will be provided, so that the planned sample size is sufficient in light of potential attrition.

Formal hypothesis testing for the purposes of labeling claims for the first secondary efficacy endpoint will only be performed if the null hypothesis for the primary efficacy endpoint is successfully rejected.

This gatekeeping approach preserves the overall type I error rate. Any other calculated p-values and confidence intervals for secondary endpoints will be nominal, without adjustment for multiple comparisons.

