All events until day x, which would be exact 6 or 12 months (180 or 365 days respective) post-implant visit would be summarized.

All events happened between day x and implant visit, which is exact 6 or 12 months (-180 or -365 days respective) pre-implant visit. Analysis will be done based on mITT population, PP population, and Cohort #1 population. Prior to the date of cut-off for the main analysis, it will be confirmed, if analysis based on PP population will be required.

This document is confidential.

7.1.6. Comparison of the number of HF Hospitalizations or Emergency Department/ Hospital Outpatient IV diuretic visits of Cohort #1 and Cohort #2 + Cohort #3 at 6 and 12 month post implant

The rate of mortality and HF hospitalizations or HF emergency department/hospital outpatient IV diuretic visits in each cohort at 6 or 12 month is calculated as the total number of observed events in each cohort divided by the (total observed exposure time/180 or 365) in each cohort from implant visit through 6 months or 12 months.

The information on mortality will be used as collected on the CRF, AE page with AE outcome = 'Death' or Study completion page with primary reason for discontinuation = 'Death'. The information on HF hospitalizations will be used as collected on the CRF, Hospitalization page, emergency department/hospital outpatient IV diuretic visits will be used as collected on the CRF, AE page with AEs resulted in = 'Emergency Department (ED) visit'/'Hospitalization'/'Urgent, unscheduled outpatient office/ practice' for AE categorized as 'Heart failure'.

The Cohort #1 and Cohort #2 + Cohort #3 subjects will then be compared with respect to rate of events per unit time using poisson regression. The test will be based on each subject's total number of events, treatment arm, and exposure time, where a subject's exposure is the time to death, early study discontinuation or 6 or 12 months, whichever is smaller.

Let λ_1 be the rate of events per 6/12 month on the Cohort #1 and let λ_2 be the rate of events per 6/12 month on the Cohort #2 + Cohort #3. The null hypothesis is $H_0: \lambda_1 \leq \lambda_2$ and the alternative hypothesis is $H_1: \lambda_1 > \lambda_2$.

The poisson regression calculation provides a one-sided p-value for the null hypothesis that the rate in the Cohort #1 is less than or equal to the rate in the Cohort #2 + Cohort #3.. The resulting p-values will be seen as explanatory.

```
proc genmod data = xxx;  
    class trt;  

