    model number of events = trt/ type3 dist= poisson offset=log(exposure_time);  
run;
```

Analysis will be done based on the Comparison population.

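### SAP 7.1.6 promises a one-sided p-value, but the program it gives tests for a difference in either direction and no step converts the result

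*SAP*

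**What the plan says.** SAP 7.1.6 covers secondary efficacy endpoint #3, the comparison of Cohort #1 (the former Control Arm) with Cohort #2 + #3 at 6 and 12 months. It defines λ1 and λ2 as the respective event rates, with H0: λ1 ≤ λ2 and H1: λ1 > λ2.

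On the p-value it states: "The poisson regression calculation provides a one-sided p-value for the null hypothesis". It spells that null out as the "null hypothesis that the rate in the Cohort #1 is less than or equal to the rate in the Cohort #2 + Cohort #3".

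The program that follows has `class trt` and then "model number of events = trt/ type3 dist= poisson offset=log(exposure_time". It contains no estimate, contrast or least-squares-means statement, no reference level for the cohort factor, and no rule that uses the sign of the difference.

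Three further statements bear on the weight of the point:

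- SAP 7.1.6, on status: "The resulting p-values will be seen as explanatory".
- SAP 2.4.2, on all secondary endpoints after the first: "Any other calculated p-values and confidence intervals for secondary endpoints will be nominal, without adjustment for multiple comparisons".
- SAP 7.1.6, on the descriptive rate: "total number of observed events in each cohort divided by the (total observed exposure time/180 or 365) in each cohort".

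**The concern.** For a two-level factor, `type3` in GENMOD gives a likelihood-ratio chi-square on 1 degree of freedom. It measures how far the two rates are apart and discards which one is higher. The default Wald chi-square in the parameter table does the same. Its p-value therefore belongs to the hypothesis λ1 = λ2 against any difference, not to the stated one-sided hypothesis. A higher event rate in Cohort #2 + #3 lies inside the stated null, yet it can produce a small type 3 p-value.

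What is at stake is correct reporting of one secondary endpoint. It is the SAP's only between-cohort test of Cohort #1 against Cohort #2 + #3, and SAP 4.6 defines the Comparison Population for it. SAP 7.1.6 asks for no rate ratio and no confidence interval, whereas 7.1.1 asks for two-sided 95% CIs. The p-value is thus the only inferential quantity specified here. The same model feeds Tables 14.2.2.3.1 to 14.2.2.3.6 and their raw SAS-output companions. One overall result, two sex groups and at least two ejection-fraction groups, from two event sources at two time points, give at least (1 + 2 + 2) × 2 × 2 = 20 p-values.

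**Working it through.** The plan gives no alpha, power or expected rates for this comparison, so there is no figure of its own to reproduce. The check is whether the coded statistic can yield the stated p-value, and how far apart the two are.

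**Inputs**

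- n1 = 85. SAP 2.2: "up to 85 subjects (cross- over from former Control Arm) will continued to be followed in Cohort #1".
- n2 = 450. SAP 2.2: "Up to 450 subjects are planned to be enrolled and successfully implanted with the Cordella PA".
- Rates are assumptions. The value 0.34 is borrowed from SAP 2.4.1, where it is the expected 6-month rate of HF hospitalization or death, not of the 7.1.6 event set. The values 0.20, 0.255 and 0.51 are chosen for contrast.
- Full exposure and no overdispersion are assumed.

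**Formulas**, with x1 and x2 events and pooled rate r0 = (x1 + x2)/(n1 + n2):

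- Type 3 statistic: G = 2[x1 ln((x1/n1)/r0) + x2 ln((x2/n2)/r0)]; type 3 p = P(χ²₁ > G).
- Stated one-sided p for H1: λ1 > λ2: z = sign(x1/n1 − x2/n2)·√G; p = 1 − Φ(z). This equals (type 3 p)/2 if the estimated λ1/λ2 exceeds 1, and 1 − (type 3 p)/2 otherwise.

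**Worked case, Cohort #2 + #3 higher.** x1 = 85 × 0.20 = 17; x2 = 450 × 0.34 = 153; r0 = 170/535 = 0.318. G = 4.963, so the type 3 p = 0.0259. The sign is negative, so the stated one-sided p = 1 − 0.0259/2 = 0.987. A subject-level Poisson regression gives the same G (4.963) and p (0.0259). The Wald version shows the same pattern: two-sided 0.038, one-sided 0.981.

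| Rates, Cohort #1 vs #2 + #3 | Events | G | Type 3 p | Stated one-sided p |
|---|---|---|---|---|
| 0.20 vs 0.34 | 17 vs 153 | 4.963 | 0.026 | 0.987 |
| 0.34 vs 0.51 | 29 vs 230 | 4.669 | 0.031 | 0.985 |
| 0.51 vs 0.34 | 43 vs 153 | 4.907 | 0.027 | 0.013 |

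Halving the type 3 p without looking at the sign does not repair this: the first row would become 0.013 instead of 0.987.

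**Frequency over repeated trials.** 200,000 Poisson simulations per row, using p < 0.05 for illustration only, since the SAP sets no threshold here:

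| True rates, Cohort #1 vs #2 + #3 | Type 3 p < 0.05 | Stated one-sided p < 0.05 |
|---|---|---|
| 0.20 vs 0.34 | 62.7% | 0.0% |
| 0.255 vs 0.34 | 25.8% | 0.1% |
| 0.34 vs 0.34 | 5.0% | 4.7% |
| 0.51 vs 0.34 | 61.0% | 71.9% |

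At equal rates, about half of the type 3 rejections (2.6 of 5.0 points) have Cohort #2 + #3 higher. The type 3 test keeps its size as a two-sided test; it is simply a test of a different hypothesis.

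**The case against.** The strongest reply is that the program is a skeleton. It has a placeholder dataset name and is not runnable as printed. The primary-endpoint program in SAP 7.1.1 is equally incomplete and has no statement testing against 0.43. On that view the text fixes the hypothesis, the snippet fixes the model, and a competent programmer would take the signed statistic from the same fit. This stands in part: a wrong number appears only if the type 3 p-value is actually reported as the one-sided one. It does not remove the gap, because the sign rule and the reference level are written nowhere.

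A second reply also stands. The cohort rates are calculated for the same comparison, and GENMOD's default parameter table carries a signed estimate. A careful reader could therefore see which cohort did worse.

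A reader might infer that the plan would present a higher event rate in Cohort #2 + #3 as evidence of benefit. The documents do not support that. The SAP calls the quantity only a one-sided p-value for λ1 ≤ λ2, attaches no claim of benefit to it, and treats it as explanatory. Nor is Cohort #1 a plain control group: its subjects are implanted, and SAP 2.2 has them unblinded and managed to target pressures.

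Finally, in the direction where Cohort #1 is higher, the type 3 p-value is a conventional and more cautious two-sided p-value. It is too large only if the one-sided hypothesis is kept.

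**Conclusion.** The mismatch is real and does not depend on any assumed rate: as written, the specified analysis does not deliver the stated p-value. The consequence is conditional. If the type 3 p-value is tabulated under the stated hypotheses, it is misleadingly small when Cohort #2 + #3 has the higher rate (0.026 instead of 0.987 in the worked case) and about double the stated value when Cohort #1 has the higher rate.

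The sizes rest on illustrative rates, 85 and 450 fully followed subjects, and pure Poisson variation. Overdispersion would change the percentages but not the sign problem. It would be wrong to infer that the trial's conclusion is at risk: no alpha or decision rule is set for this comparison, and formal testing for labelling among the secondary efficacy endpoints covers only the first. This is a minor correction.

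**What to change.** Make the text and the program in SAP 7.1.6 agree, in one of two ways:

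1. Keep the one-sided hypotheses. Fix the cohort reference level, add an `estimate` statement (or `lsmeans` with `diff`) for log(λ1/λ2), and take the one-sided p-value from the signed statistic: p/2 if the estimated ratio exceeds 1, otherwise 1 − p/2. State that rule in the text.
2. Restate the test as two-sided for λ1 = λ2. The type 3 p-value is then the right one, and the sentence on one-sidedness is removed.

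In both cases, report the rate ratio with its two-sided 95% CI in Tables 14.2.2.3.1 to 14.2.2.3.6, so that direction and precision appear beside the p-value. The cost is about one program line and one SAP sentence, with no new data and no effect on subjects.

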7.1.7. Change of NT-proBNP from Baseline through 6 and 12 months

Change of NT-proBNP from baseline through 6 and 12 months will be presented by means of descriptive statistics at all study visits as described in [Appendix 1: Time and Event Schedule](#).

Analysis will be done based on mITT population, PP population, and Cohort #1 population. Prior to the date of cut-off for the main analysis, it will be confirmed, if analysis based on PP population will be required.

7.1.8. Combined outcome of: a. First and recurrent HF Hospitalizations b. HF Emergency Department/ Hospital Outpatient IV diuretic visits c. all-cause mortality at 6 months

Number of total events will be calculated as the sum of the number of HF hospitalizations, HF emergency department/hospital outpatient IV diuretic visits and all-cause mortality. Both first and recurrent events will contribute to the total number. All events will be equal weighting.

This endpoint will be analyzed similarly as the primary endpoint in Section [7.1.1](#).

Analysis will be done based on mITT population, PP population and Cohort #1 population. Prior to the date of cut-off for the main analysis, it will be confirmed, if analysis based on PP population will be required.

This document is confidential.

7.1.9. Heart failure hospitalization or HF Emergency Department / Hospital Outpatient IV diuretic visits at 6 and 12 months

Number of total events will be calculated out of number of HF hospitalizations or HF emergency department/hospital outpatient IV diuretic visits at 6 and 12 months. First and recurrent events will account to the total number. All events will be equal weighting.

This endpoint will be analyzed similarly as the primary endpoint in Section [7.1.1](#).

In addition, time to first HF hospitalization/ time to first HF emergency department/hospital outpatient IV diuretic visit in days will be defined as the time from date of Implant visit to the date of the event. In case of no event during the observation period, subject will be censored on the last available date.

Definition of time to first HF hospitalization (days):

In case of event, time to first HF hospitalization = [(Date of event – date of Implant visit) + 1]

In case of no event, time to HF hospitalization = [(Date of last available date – date of Implant visit) + 1], this data will be censored.

Definition of time to first HF emergency department/hospital outpatient IV diuretic visit (days):

In case of event, time to first HF emergency department/hospital outpatient IV diuretic visit = [(Date of event – date of Implant visit) + 1]

In case of no event, time to HF emergency department/hospital outpatient IV diuretic visit = [(Date of last available date – date of Implant visit) + 1], this data will be censored.

Median duration of time to first HF hospitalization, time to first HF emergency department/hospital outpatient IV diuretic visit and respective 95% CIs will be reported using Kaplan Meier estimator and Kaplan Meier plot.

```
proc lifetest data = xxx  
    time days * censor(1);  
run;
```

Time to HF hospitalization and time to HF emergency department/hospital outpatient IV diuretic visit will be listed.

Analysis will be done based on mITT population, PP population, and Cohort #1 population. Prior to the date of cut-off for the main analysis, it will be confirmed, if analysis based on PP population will be required.

7.1.10. Cardiac and all-cause mortality

Time to all-cause mortality in days will be defined as the time from date of Implant visit to the date of the death. In case of no death during the observation period, subject will be censored on the last available date known alive.

Similarly, time to cardiac mortality in days will be defined as the time from date of Implant visit to the date of the cardiac death. In case of no cardiac death during the observation period, subject will be censored on the last available date known without cardiac death event.

Definition of time to death (days):

In case of event, time to death = [(Date of death – date of Implant visit) + 1]

In case of no event, time to death = [(Last available date – date of Implant visit) + 1], this data will be censored.

Definition of time to cardiac death (days):

This document is confidential.

In case of event, time to cardiac death = [(Date of cardiac death – date of Implant visit) + 1]

In case of no event, time to cardiac death = [(Last available date without cardiac death event – date of Implant visit) + 1], this data will be censored.

Time to death/cardiac death will be listed and summarized by descriptive statistics.

Median duration of time to death and respective 95% CIs will be reported using Kaplan Meier estimator and Kaplan Meier plot.

```
proc lifetest data = xxx  
    time days * censor(1);  
run;
```

Analysis will be done based on mITT population, PP population, and Cohort #1 population. Prior to the date of cut-off for the main analysis, it will be confirmed, if analysis based on PP population will be required.

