10.4 Additional Secondary Efficacy Endpoints

The first secondary efficacy endpoint is incidence of HF Hospitalizations or all-cause mortality at 12 months compared to a PG.

The mean 12 month event rate from the meta-analysis of prior control studies is 0.75, or 0.70 on an adjusted basis to account for SGLT-2i inclusion in the guidelines^b. A 12 month event rate of 0.70 represents a value just below the highest event rate observed across the CardioMEMS treatment studies (0.73 in MEMS-HF) and the upper bound of the overall meta-analytic treatment estimate (0.74). Taking the totality of results from the meta-analysis of active treatment trials, individual

^b Adjustment applied assuming 50% use of SGLT2i at the average hazard ratio observed across EMPEROR Preserved, EMPEROR REDUCED, DAPA-HF for NYHA III subjects.

results of active treatment trials, as well as the meta-analysis of control trials, we set the secondary endpoint performance goal (PG₁₂) at 0.70.

Furthermore, the mean 12 month event rate from the meta-analysis of prior treatment studies is 0.64, with both the CHAMPION (0.6) and GUIDE-HF (0.52, NYHA class III) treatment groups with event rates lower than the mean. The lowest 12 month event rate across CardioMEMS control studies of 0.63 occurred in GUIDE-HF (NYHA class III only), where modest use of SGLT2i occurred during the trial. We conservatively adjust this lowest observed control event rate down to 0.59 to account for increased SGLT2i utilization.

The table below outlines the data sources used to derive a PG for this endpoint.

Active Treatment - updated 12 Month Rates with calculation details

Study/Publication	Number of Subjects ¹	Events	Rate ²	Details
CHAMPION ⁵³	270	162	0.60	- HFH rate of 0.46, yielding approx. 124 events - Mortality rate of 0.14, yielding approx. 38 events - Total events = 124 + 38
MEMS PAS ⁴⁴	1200	840	0.70	- HFH rate of 0.54, yielding 648 events - Mortality rate of 0.16, yielding 192 events - Total events = 648 + 192
MEMS-HF ⁴⁶	234	171	0.73	- HFH rate of 0.60, yielding 140 events - Mortality rate of 0.13, yielding approx. 30 events - Total events = 140 + 31
GUIDE-HF ⁵¹ – NYHA class III only	322	167	0.52	- - HFH rate of 0.431 + plus death rate of 0.0897 - Composite rate = 0.52 - Total events = 322 subjects x 0.52
Estimate CI			0.64 (0.55, 074)	

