8.8. Physical Examination

Complete physical examinations including body systems: general appearance, dermatological, lymphatic, head/ears/eyes/nose/throat (HEENT), chest/lungs, cardiovascular, abdomen, genitourinary/reproductive, musculoskeletal/extremities, neurologic/psychiatric and other) will be conducted at screening visits, Abbreviated physical examination will be conducted at all study visits as described in [Appendix 1: Time and Event Schedule](#), collecting only the changes from screening assessment.

In addition, chest circumference will be collected at screening.

Physical examination data will be summarized at screening visit, all data will be listed only.

This document is confidential.

9. Interim Analyses

Interim analysis is not planned.

This document is confidential.

10. Changes from Analysis Planned in Protocol

During the preparation of the SAP, it was realized that some additional analysis outside the protocol is needed. The respective analysis were introduced in the respective sections and are summarized below.

- 1) It was clarified that cardiac and all-cause mortality will be analyzed at 6 and 12 months post-implant visit, to be consistent with other efficacy analyses.
- 2) Two enrollment stopping rules will be considered during the study, both rules will be applied independently of each other and as well independent of the treatment group, see section 2.2. The enrollment stopping rules will ensure enrollment of sufficient number of subjects of certain population: at least 30 % women and at least 45 % HFpEF. This approach was previously confirmed by Sponsor with FDA.
- 3) Subgroup analysis was not clearly defined in the protocol: two population groups are of interest and were introduced in Section 5.6. This analysis is in line with the introduction of the enrollment stopping rules for the same populations, see Section 2.2.

This document is confidential.

11. Reference List

1. DSMB Statistical Analysis Plan Version 3.1 dated 07-Feb-2022
2. DSMB charter Version 4.0 dated 04-Mar-2022
3. Abraham, W. T., Adamson, P. B., Bourge, R. C., Aaron, M. F., Costanzo, M. R., Stevenson, L. W., CHAMPION Trial Study Group. (2011). Wireless pulmonary artery haemodynamic monitoring in chronic heart failure: a randomized controlled trial. *Lancet*, 377, 658-666.

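### SAP 7.1.10 does not produce the 6- and 12-month mortality analysis that SAP 10 says will be done: cardiac mortality at either time, and 12-month all-cause mortality with a confidence interval, are not specified

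*SAP*

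**What the plan says.** Cardiac and all-cause mortality is secondary efficacy endpoint 7 in SAP 3.3. Among the changes from the protocol, SAP 10 lists: "It was clarified that cardiac and all-cause mortality will be analyzed at 6 and 12 months post-implant visit".

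SAP 7.1.10 defines time to death as the days from implant to death. For subjects without the event it runs to the last available date and is flagged as censored. Time to cardiac death is built the same way. The planned output is:

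- "Time to death/cardiac death will be listed and summarized by descriptive statistics". Under SAP 5.1, descriptive statistics for a continuous variable are n, mean, SD, median, minimum and maximum.
- "Median duration of time to death and respective 95% CIs will be reported using Kaplan Meier estimator and Kaplan Meier plot". This sentence covers time to death; no median is stated for cardiac death.

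The sample code requests no time point, and the titles of Tables 14.2.2.7.x name none.

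Some mortality output is planned elsewhere. SAP 7.1.1 includes the number of deaths to day 180 in the primary table. SAP 7.1.3 analyses CEC-adjudicated all-cause mortality on its own by the primary Poisson method, shown in Table 14.2.1.1.12.

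**The concern.** A named secondary endpoint has a stated analysis time, and the section that should deliver it does not. Programmers following 7.1.10 would report two kinds of figure. One is a median that is probably not estimable. The other is a mean and median of a variable that is, for most subjects, time under observation. The second is the more troublesome, because it looks like a survival result. Implants ran from the fourth quarter of 2019 to an estimated first quarter of 2023 (protocol 6.3), so follow-up at the main cut-off differs by years between subjects, and the average would follow the accrual pattern more than the death rate.

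**Working it through.** **1. Inputs.** The plan gives no median survival for this trial, so the death rates come from its planning tables (protocol 10.3 and 10.4; SAP 2.4.1 and 2.4.2). The highest 12-month figure is "Mortality rate of 0.16, yielding 192 events", and 0.16 × 1200 = 192 reproduces. CHAMPION has 0.14 (0.14 × 270 = 37.8, shown as about 38) and MEMS-HF 0.13 (0.13 × 234 = 30.4, shown as about 30). The lowest is GUIDE-HF NYHA III, with 0.089 in the 6-month table and 0.0897 in the 12-month table. The range used is 0.089 to 0.16, in 450 implanted subjects.

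**2. Median survival.** With constant hazard h = −ln(1 − m), the median is ln 2 / h.

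| 12-month mortality m | h per year | Median (years) | Survival at 6 months | 12 months | 3 years |
|---|---|---|---|---|---|
| 0.089 | 0.0932 | 0.693/0.0932 = 7.4 | 95.4% | 91.1% | 75.6% |
| 0.16 | 0.1744 | 0.693/0.1744 = 4.0 | 91.7% | 84.0% | 59.3% |

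Reading the tabled figures as hazards instead gives ln 2/0.089 = 7.8 and ln 2/0.16 = 4.3 years, with the same conclusion.

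**3. Chance that the Kaplan-Meier median is reached.** Simulation of 450 subjects, assuming 2% dropout per 6 months:

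| Follow-up (assumed) | m = 0.089 | m = 0.16 |
|---|---|---|
| Main cut-off, 0.5 to 3.75 years | 0 | about 28% |
| 3 years for all | 0 | 0 |
| 5 years for all | 0 | about 100% |

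**4. What the mean of the time variable measures.** Take follow-up c uniform between a and b years, with no dropout. The mean of the smaller of death time and c is (1/h) × [1 − (e^(−ha) − e^(−hb)) / (h(b − a))].

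- m = 0.089, a = 0.5, b = 3.75: (1/0.0932) × [1 − (0.9545 − 0.7050)/0.3029] = 1.89 years.
- m = 0.16, same follow-up: (1/0.1744) × [1 − (0.9165 − 0.5201)/0.5666] = 1.72 years.
- m = 0.16, cut-off one year later (a = 1.5, b = 4.75): (1/0.1744) × [1 − (0.7699 − 0.4368)/0.5666] = 2.36 years.
- No deaths, first follow-up: (0.5 + 3.75)/2 = 2.13 years.

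Nearly doubling mortality moves the mean by 0.17 years. Moving the cut-off by one year moves it by 0.64 years, in the direction that looks like better survival.

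**5. Promise against output.**

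| Quantity | At 6 months | At 12 months |
|---|---|---|
| All-cause mortality | Death count in the primary table; CEC-adjudicated Poisson rate (Table 14.2.1.1.12) | At most a death count, if the similar handling of the 12-month composite in SAP 7.1.4 extends to component counts; no separate table or interval |
| Cardiac mortality | None specified | None specified |

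**6. Feasibility of direct estimates.** The half-width is 1.96 × √(p(1 − p)/450), ignoring dropout. At 6 months, p = 1 − 0.911^0.5 = 0.046 to 1 − 0.84^0.5 = 0.083 (about 20 to 38 deaths) gives 1.9 to 2.6 points. At 12 months, p = 0.089 to 0.16 (about 40 to 72 deaths) gives 2.6 to 3.4 points. Both are precise enough to report.

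**The case against.** The strongest reply is that mortality is not left without a number. All-cause mortality at 6 months is produced twice outside 7.1.10, and Kaplan-Meier curves are planned for all-cause and cardiac death, from which 6 and 12 months can be read. These are also secondary summaries, nominal and outside the gatekeeping. This stands in part. It rules out saying that the plan yields no mortality result at the main analysis. It does not supply cardiac mortality or a 12-month all-cause estimate with an interval, and reading a curve is not a commitment to report a value.

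It could also be said that the descriptive statistics are meant for the deaths only. The definition in 7.1.10 does not say so, and times among the deaths alone still would not estimate mortality.

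Three stronger readings are tempting and are not supported:

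- *That time to first HF event has the same defect.* SAP 7.1.9 does plan a median ("Median duration of time to first HF hospitalization"), but it also says "This endpoint will be analyzed similarly as the primary endpoint in Section" 7.1.1, so 6- and 12-month event rates are already planned, and it asks only for a listing of the event times.
- *That the first-HF-hospitalisation median cannot be reached.* Censoring is at the last available date. At 0.431 to 0.60 hospitalisations per subject-year the median is about 1.2 to 1.6 years without over-dispersion, and 1.7 to 2.3 years with an assumed dispersion of 1. It is in doubt at the main cut-off only under strong dispersion.
- *That the death median is never reached.* At 16% mortality it falls within the protocol's 5 years of follow-up.

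**Conclusion.** The point holds for SAP 7.1.10. The section does not carry out what SAP 10 states: cardiac mortality at 6 and 12 months, and 12-month all-cause mortality with a confidence interval, are not specified. Its median for death is expected at about 4.0 to 7.4 years, beyond 12 months and beyond Year 3. Its descriptive statistics of a mostly censored variable respond more to the cut-off date than to mortality.

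This rests on a constant hazard, on mortality in the range of the planning tables, and on follow-up ending at Year 3 as the SAP's final analysis describes. The main cut-off follow-up and the dropout rate are assumptions. The gap between SAP 10 and 7.1.10 does not depend on any of them. The primary and first secondary efficacy tests are unaffected.

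**What to change.** In SAP 7.1.10 and Tables 14.2.2.7.x:

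- Report all-cause mortality as one minus Kaplan-Meier, with 95% confidence interval and number at risk, at day 180 and day 365.
- Report cardiac mortality at the same days as cumulative incidence, with non-cardiac death as a competing event. One minus Kaplan-Meier would overstate it.
- Give the median only if it is reached.
- Delete the descriptive statistics of time to death and cardiac death; keep the listing.

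The SAP already uses Kaplan-Meier estimates at 6 months with 95% intervals for the primary safety endpoints (8.1.1), so the all-cause part needs no new method. Adding day-180 and day-365 estimates to the Kaplan-Meier output in 7.1.9 is optional. The cost is SAP wording and table shells; no new data and no change to sample size or testing.
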